A total of 100 veterans with moral injury were randomized 1:1 to either the IOK or PCT control arm within strata therapist treatment site (one of three locations) within randomly generated block sizes (4 and 6). IOK is a ten session individual psychotherapy, with 60- to 90-minute appointments conducted in-person or by video. PCT was matched for number and duration of treatment sessions. Primary and secondary self-report outcome measures were completed at baseline, mid-treatment, post-treatment and at six-month follow-up and the clinician diagnosed secondary outcome of PTSD severity (CAPS-5) was completed at baseline and post-treatment.

All participants randomized to treatment were included in the intent-to-treat analyses. Twelve of these individuals dropped out during treatment and 88 individuals completed study treatment. Of the treatment completers, one individual chose not to complete the self-report measures (i.e., WHOQOL-BREF, PCL-5, TRGI, and BSI) at the post-treatment time point and a different individual opted out of the post-treatment diagnostic interview (CAPS-5). As such, complete data for 87 responses through the post-treatment time point were included in the analyses.

Further, five of the 88 individuals that completed treatment were lost to follow-up and analyses of these data included complete data for 83 participants.

Statistical Analysis Plan: The primary and secondary outcome variables were analyzed with separate linear mixed models on the intent-to-treat sample, with participants as a random effect and fixed effects for treatment group (IOK, PCT), time point (baseline, mid-treatment, post-treatment, six-month follow-up), therapist treatment site (SFVAHCS, JJPVAMC, DVAMC), and the group-by-time interaction. Time point was treated as a categorical variable to avoid assumptions of linearity or any other functional form for outcome variables over time. Treatment effects were defined as the difference between treatment groups at the post-treatment time point, after adjusting for therapist site. IOK treatment durability was assessed using simple marginal contrasts comparing outcomes at the post-treatment to the follow-up time point.

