Results: A total of 100 participants were randomized to study treatment and included in the intent-to-treat analysis (IOK=49; PCT=51). Participants ranged in age from 28 to 82 years (M=48.4 years); 98% were male (n=98) and 2% were female (n=2); 68% were Caucasian (n=68), 25% were Black/African American (n=25), 1% were Asian (n=1), 1% were American Indian or Alaska Native (n=1), 4% identified as multiracial or other (n=7), and 1% did not report their race (n=1). A total of 19% were Latino/Hispanic (n=19).

Participants randomized to IOK (n=49) reported statistically significant improvement on self-report measures of PTSD severity (p=.006) and guilt (p=.043) compared to veterans that were assigned to PCT (n=51). Furthermore, participants in the IOK arm continued to report greater improvement in self-reported PTSD (p=.008) and guilt (p=.028) at the six-month follow-up time point relative to the PCT arm. These results indicate that IOK treatment gains seen at post-treatment were maintained during the follow-up period. Further, veterans in the IOK group reported greater improvement in general mental health symptoms at six-month follow-up (p=.016) compared to the PCT group. There were no differences between groups on the primary (WHOQOL-BREF) or secondary (CAPS-5) outcomes, although both groups improved on these measures.

References:

- 2. Kang, H. K., Natelson, B. H., Mahan, C. M., Lee, K. Y., & Murphy, F. M. (2003). Post-traumatic stress disorder and chronic fatigue syndrome-like illness among Gulf War veterans: A population-based survey of 30,000 veterans. *American Journal of Epidemiology*, 157(2), 141-148.
- 3. Tanielian, T. L., Jaycox, L., & Rand Corporation. (2008). *Invisible wounds of war:*Psychological and cognitive injuries, their consequences, and services to assist recovery. Santa Monica, CA: RAND.
- Department of Veterans Affairs. (2015). Analysis of VA health care utilization among Operation Enduring Freedom (OEF), Operation Iraqi Freedom (OIF), and Operation New Dawn (OND) veterans. Retrieved from https://www.publichealth.va.gov/docs/epidemiology/healthcare-utilization-report-fy2015qtr1.pdf

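### The post-treatment contrast is adjusted for site but not for the baseline score already collected: valid, but less precise than a constrained-baseline estimate on the same 100 participants

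*Combined protocol and SAP*

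**What the plan says.** The combined document specifies one linear mixed model per outcome, "with participants as a random effect and fixed effects for treatment group (IOK, PCT), time point", therapist site and group-by-time. Baseline is one of the four levels of time. It is therefore an outcome row, and each arm has its own baseline mean. No baseline covariate and no common-baseline constraint is stated. The effect is then defined: "Treatment effects were defined as the difference between treatment groups at the post-treatment time point, after adjusting for therapist site".

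Methods shows that baseline scores exist for every outcome. The self-report measures were taken at all four visits, and the "clinician diagnosed secondary outcome of PTSD severity (CAPS-5) was completed at baseline and post-treatment". On the analysis set it says: "All participants randomized to treatment were included in the intent-to-treat analyses".

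For six months the plan gives only a durability statement: "IOK treatment durability was assessed using simple marginal contrasts comparing outcomes at the post-treatment to the follow-up time point". Results nevertheless compares the arms at that visit, saying that IOK participants "continued to report greater improvement in self-reported PTSD (p=.008) and guilt (p=.028) at the six-month follow-up time point", and it gives a further between-arm p-value of .016 for general mental health symptoms. On the main outcomes it says: "There were no differences between groups on the primary (WHOQOL-BREF) or secondary (CAPS-5) outcomes".

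**The concern.** A participant random effect is easily taken to mean that the post-treatment comparison is adjusted for baseline. With free arm means at baseline it is not. With complete data the contrast is simply the site-adjusted difference in post-treatment means, whatever the within-person correlation. With missing data, baseline helps a little to predict the unobserved post-treatment scores, and that is all.

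Validity is not at stake. Two things are:

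- **Precision.** A null result on a primary outcome can be read only through its interval. None is given for WHOQOL-BREF or CAPS-5, and the planned interval is wider than the data require.
- **Chance imbalance.** Baseline means and SDs by arm are not given, so a reader cannot tell whether the planned estimate carries an imbalance.

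There is also a gap in wording. The plan defines the treatment effect only at post-treatment, so the contrast behind the six-month between-arm p-values is not identified.

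**Working it through.** The documents give no SD, correlation, power or target effect, so there is no design figure to reproduce.

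**Inputs from the documents.** 49 IOK and 51 PCT at baseline; three sites; 12 dropouts (100 − 12 = 88 completers); 88 − 1 = 87 observed at post-treatment, for the self-report measures and for CAPS-5; 88 − 5 = 83 at six months.

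**Assumptions.** Unit SD at every visit; equal correlation ρ between visits, set to 0.3, 0.5 and 0.7; data missing at random; the 87 split about evenly between arms (43 and 44 below).

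**CAPS-5 (two visits), by hand, leaving out the small cost of the site terms.** Let A = 1/43 + 1/44 = 0.04598 (observed at post-treatment) and B = 1/49 + 1/51 = 0.04002 (observed at baseline).

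- Planned contrast: variance = (1 − ρ²)A + ρ²B
- Common baseline mean: variance = (1 − ρ²)A
- Change from baseline: variance = (1 − ρ²)A + (1 − ρ)²B

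| ρ | Planned: variance, SE | Common baseline: variance, SE | Ratio to planned | Change: variance, SE | Ratio to change |
|---|---|---|---|---|---|
| 0.3 | 0.0454, 0.213 | 0.0418, 0.205 | 0.92 | 0.0615, 0.248 | 0.68 |
| 0.5 | 0.0445, 0.211 | 0.0345, 0.186 | 0.78 | 0.0445, 0.211 | 0.78 |
| 0.7 | 0.0431, 0.208 | 0.0235, 0.153 | 0.54 | 0.0271, 0.164 | 0.87 |

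The planned SE barely moves with ρ, so the planned contrast takes little from baseline.

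**Self-report outcomes (four visits).** Exact generalized least squares with site in the model and the trial's missing-data counts gives:

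| ρ | Post-treatment: planned | Common baseline | Variance ratio | Six months: planned | Common baseline |
|---|---|---|---|---|---|
| 0.3 | 0.213 | 0.204 | 0.92 | 0.217 | 0.209 |
| 0.5 | 0.210 | 0.185 | 0.77 | 0.214 | 0.189 |
| 0.7 | 0.207 | 0.152 | 0.54 | 0.209 | 0.155 |

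The timing of dropout is not given. With 0, 6 or all 12 dropouts leaving before mid-treatment, the post-treatment SEs change by at most 0.002.

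**Interval width at post-treatment.** With a Kenward-Roger correction the common-baseline SE is 0.205, 0.186 and 0.153. The 95% half-width goes from 0.42, 0.42 and 0.41 SD (planned) to 0.41, 0.37 and 0.30 SD.

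**Chance imbalance.** The SE of a baseline difference is √B = 0.20 SD. The planned estimate moves by ρ times the imbalance, so a 1-SE imbalance moves it by 0.06, 0.10 or 0.14 SD.

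**Does the added model hold its error rate?** An unstructured REML fit was simulated under the null, with 20,000 trials per scenario. Type I error for a nominal 5% test was 5.2% to 5.7% with a fixed critical value of 1.98, and 4.8% to 5.3% with Kenward-Roger. When correlations decay over time, a common baseline mean fitted with only a random intercept rejected in 8.0% of 5,000 null trials.

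**Six-month candidates.** The SEs at ρ = 0.3, 0.5 and 0.7 are 0.217, 0.214 and 0.209 for the level difference; 0.251, 0.214 and 0.166 for change from baseline; and 0.258, 0.218 and 0.169 for change from post-treatment. These answer different questions with different precision, so the text needs to name the one used.

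**The case against.** The best defence is that nothing is wrong. A mixed model with categorical time, all randomized participants and the stratification factor is an accepted analysis, and the trial is finished. A more efficient estimator added now is post hoc and cannot replace the planned result. This stands, and it is why the point concerns precision only.

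Second, the gain depends on a correlation that the documents do not give. At 0.3 the SE falls by only about 4% (1 − 0.204/0.213), against 12% at 0.5 and 27% at 0.7. This also stands: the direction is certain, the size is not.

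Third, Results speaks of improvement at post-treatment as well. If the reported p-values came from change-from-baseline contrasts, baseline was already used as a change score, and the gain is then larger at low correlation and smaller at high. That is a fair caution about the reported results. It does not alter what the plan defines, and the common-baseline estimate is still more precise, with variance ratios of 0.68, 0.78 and 0.87 in the hand calculation.

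Fourth, the planned model already includes all 100 participants. That is correct. The gain comes from the equal-baseline constraint, which randomization justifies, and not from a larger sample.

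**Conclusion.** The point holds and should be fixed, as a matter of precision and reporting. The contrast the plan defines is valid, but it leaves unused most of the information in the baseline scores. A common baseline mean would cut its variance by about 8%, 23% and 46% at correlations of 0.3, 0.5 and 0.7. This assumes equal variances and correlations over visits, data missing at random, and a near-even split of the missing participants. Whether a baseline imbalance occurred cannot be told from the documents, and nothing here shows that any conclusion would change. That the six-month contrast is not identified follows from the text alone.

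**What to change.** 1. Report, by arm, the baseline mean and SD of each outcome, and the planned contrast with its 95% interval. The planned contrast remains the planned analysis.
2. Beside it, give one constrained-baseline estimate per outcome and time point, labelled post hoc. Take all visits, baseline included, as outcomes, with categorical time, site as a fixed effect, group effects at post-baseline visits only, an unstructured covariance, REML, and Kenward-Roger standard errors and degrees of freedom. Use four visits for the self-report outcomes (post-treatment and six-month differences) and two for CAPS-5 (post-treatment difference). Everyone with a baseline score stays in, which agrees with the intent-to-treat statement. Do not impose the common baseline with a random intercept alone.
3. State which contrast gave the six-month between-arm p-values: the level difference, change from baseline or change from post-treatment. The same sentence can confirm the contrast behind the post-treatment p-values.

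The cost is a re-run on existing data and a few lines of text. The downside is about nine extra estimates (4 self-report outcomes × 2 times + 1 for CAPS-5, if each gives one score), chosen after the results were known. They should be given for every outcome and read as supportive only.

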Objectives: The first aim of this project was to assess the efficacy of an individual treatment for PTSD stemming from moral injury called IOK. The primary outcome measure assessed self-reported psychosocial functioning (World Health Organization Quality of Life-BREF; WHOQOL-BREF). The secondary outcome measures examined clinician-assessed PTSD severity (Clinician Administered PTSD Scale for DSM-5; CAPS-5)¹² and self-report measures of PTSD (PTSD Checklist for DSM-5; PCL-5)¹³, guilt (Trauma-related Guilt Inventory; TRGI)¹⁴, and other mental health symptoms (Brief Symptom Inventory; BSI). Our second aim was to determine whether IOK gains made by veterans in treatment were durable, as measured by a six-month follow-up assessment of the self-report outcomes (i.e., WHOQOL-BREF, PCL-5, TRGI, and BSI).

Design: The study was a parallel design, randomized, controlled trial to test the efficacy of IOK, compared to a present-centered therapy (PCT) control condition. PCT has been used as a

comparison treatment in prior PTSD research trials. ¹⁶ To evaluate the durability of IOK gains, veterans also participated in a six-month follow-up visit to complete primary and secondary self-report outcome measures.

Methods: The study was managed by the principal investigator and research staff at the San Francisco VA Health Care System (SFVAHCS) and all recruitment, screening and data collection procedures were conducted by researchers at the James J. Peters VA Medical Center (JJPVAMC) in the Bronx, NY or the Durham VA Medical Center (DVAMC) in Durham, NC. Veterans between 18-82 years of age living in the continental U.S. were recruited through direct mailings, advertisements, and referrals from VA clinicians or other VA research studies. Interested veterans participated in an initial brief phone screen to ensure they met preliminary criteria. Those who passed the phone screen were invited to an in-person or video appointment to learn more about the study and complete consent procedures prior to additional screening. Participants completed demographic and medical history questionnaires, and a clinician-administered, mental health diagnostic interview (Structured Clinical Interview for DSM 5 [SCID-5]¹⁷ and CAPS-5). These diagnostic interviews were repeated at post-treatment. Veterans that passed the diagnostic interview were randomized to treatment. Study clinicians were clinical staff at one of the three study sites (SFVAMC, JJPVAMC, DVAMC).

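### The conclusion that IOK gains were maintained rests on six-month IOK-versus-PCT p-values; the planned post-treatment-to-follow-up contrast is not reported

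*Combined protocol and SAP*

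**What the plan says.** The Objectives section sets durability as the second aim: "Our second aim was to determine whether IOK gains made by veterans in treatment were durable, as measured by a six-month follow-up assessment". The measures named there are the four self-report outcomes, WHOQOL-BREF, PCL-5, TRGI and BSI. The Design section repeats the purpose: "To evaluate the durability of IOK gains, veterans also participated in a six-month follow-up visit".

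The Statistical Analysis Plan section then separates two quantities:

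- The treatment effect: "Treatment effects were defined as the difference between treatment groups at the post-treatment time point, after adjusting for therapist site".
- Durability: "IOK treatment durability was assessed using simple marginal contrasts comparing outcomes at the post-treatment to the follow-up time point".

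The Results section reports that IOK participants "continued to report greater improvement in self-reported PTSD (p=.008) and guilt (p=.028) at the six-month follow-up time point relative to the PCT arm". The next sentence is the conclusion: "These results indicate that IOK treatment gains seen at post-treatment were maintained during the follow-up period". A six-month between-arm p-value for BSI (.016) comes after it. No estimate, interval or p-value for change from post-treatment to six months is given for any outcome.

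**The concern.** The six-month p-values are neither of the two quantities that the analysis section defines. They compare arms at one visit, whereas durability compares visits. The Results nevertheless present them as the evidence that gains were maintained.

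A reader will take the sentence to mean that IOK participants held their improvement on PCL-5 and TRGI for six months. Durability is one of only two aims, and the primary outcome showed no difference between arms, so this is one of the trial's more prominent positive messages. If the comparison behind it does not answer the question, Aim 2 has no printed answer.

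**Working it through.** **1. What a six-month between-arm difference can show.** Write the IOK mean as I(post) and I(6m), and the PCT mean as P(post) and P(6m). The printed six-month test concerns I(6m) − P(6m). Durability within IOK concerns I(6m) − I(post). Add the same shift c to both arms after treatment:

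- between arms: [I(6m) + c] − [P(6m) + c] = I(6m) − P(6m), unchanged;
- within IOK: the change moves by the full c.

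The same p-values therefore fit maintenance, further gain or partial loss. As a hypothetical only, suppose both arms worsened by 0.5 SD. The between-arm p-values would stay as printed. The within-IOK z would be 0.5 / √(2(1−r)/n), which runs from 3.04 (n = 37, r = 0.5) to 5.30 (n = 45, r = 0.8). Nothing in the document suggests that this happened.

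**2. What the printed p-values imply about the difference between arms.** The document gives no means, SDs or intervals, so there is no stated estimate to reproduce. Convert each two-sided p to t, then use d = t·√(1/n₁ + 1/n₂). The arm splits are assumed: 43/44 at post-treatment (87 participants) and 41/42 at six months (83).

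| Outcome | Visit | p | t | d (SD) |
|---|---|---|---|---|
| PCL-5 | post-treatment | .006 | 2.82 | 0.60 |
| PCL-5 | six months | .008 | 2.72 | 0.60 |
| TRGI | post-treatment | .043 | 2.05 | 0.44 |
| TRGI | six months | .028 | 2.24 | 0.49 |

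If the p-values test change from baseline and not level, multiply by √(2(1−r)), which is 1.00 at r = 0.5 and 0.63 at r = 0.8. On either footing the separation between arms looks roughly constant. None of these figures says how far either arm moved after treatment.

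**3. How precise the planned contrast would be.** Inputs from the Methods and Results sections:

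- 100 randomized (IOK 49, PCT 51); 100 − 12 dropouts = 88 completers.
- Follow-up: "five of the 88 individuals that completed treatment were lost to follow-up and analyses of these data included complete data for 83 participants", so 88 − 5 = 83.
- At post-treatment, "one individual chose not to complete the self-report measures". If that person is not among the five lost, 83 − 1 = 82 have self-report data at both visits.
- The split by arm is not given. IOK lies between 82 − 51 = 31 and 49.

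These counts assume that the 12 dropouts gave no later data. Half-width of the 95% CI in SD units = t(.975, n−1)·√(2(1−r))/√n, with an assumed correlation r between visits:

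| IOK n | r = 0.5 | r = 0.8 |
|---|---|---|
| 31 | 0.367 | 0.232 |
| 41 | 0.316 | 0.200 |
| 49 | 0.287 | 0.182 |

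With the larger degrees of freedom of a pooled mixed model (about 240, assumed), n = 41 gives 0.308 to 0.195. A weaker correlation widens the interval: r = 0.3 at n = 41 gives 0.37. With intervals of this width, a non-significant contrast would not by itself show maintenance. The estimate and its interval are needed.

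**The case against.** The strongest reply is that gains may here mean the advantage over PCT. The post-treatment result is introduced as improvement relative to PCT, the six-month result is worded the same way, and the analysis section defines treatment effects between arms. In a randomized trial a persisting between-arm difference is relevant evidence, since uncontrolled change within one arm mixes treatment with natural course. On that reading the sentence agrees with the PCL-5 and TRGI p-values. This stands as far as it goes. But Aim 2 concerns the gains veterans made in treatment, and it would then be unanswered. Nor are two significant tests at separate visits an estimate of change between visits.

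Other points also have weight:

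- The contrast is said to have been assessed, so it may well have been run. The plan is not faulty here; the fault is in what is reported and what is inferred from it.
- If greater improvement means change from baseline, the Results imply that some IOK improvement remained at six months. They do not say how much of the post-treatment gain was kept.
- The analysis section does not say whether the contrast is within IOK or between arms. Either way it compares two visits, and neither version is printed.
- The back-calculated differences rest on assumptions and do not bear on change within IOK. They are illustration only.

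**Conclusion.** The concern holds. As written, the sentence draws a conclusion about durability from a comparison that cannot identify it, and the planned contrast is not reported for any of the four Aim 2 outcomes. For PCL-5 and TRGI this is an inference from the wrong comparison. For WHOQOL-BREF and BSI, which the sentence does not clearly cover, it is an omission.

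The printed results support a narrower statement: an IOK advantage on PCL-5 and TRGI was still present at six months. They set no limit on how much IOK participants lost or gained after treatment; the planned contrast would do so to within roughly ±0.2 to ±0.4 SD. That range depends on the assumed arm split and correlation, and on simple t formulas that only approximate the mixed model. The conclusion itself depends on none of these. It does not imply that gains were lost, and it leaves the null result on the primary outcome untouched.

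**What to change.** 1. From the mixed models already fitted, report the within-IOK change from post-treatment to six months, with a 95% CI, for WHOQOL-BREF, PCL-5, TRGI and BSI.
2. State that the within-IOK reading of the contrast is a clarification made after the results were known.
3. Base the durability statement on those estimates and intervals, not on non-significance. No margin was set in advance and none is required, so the wording should describe how much change the interval allows.
4. Report the six-month IOK–PCT differences (PCL-5 .008, TRGI .028, BSI .016) separately, as between-arm comparisons at follow-up.

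If the contrast is not reported, replace the sentence with one saying only that the difference between IOK and PCT on PCL-5 and TRGI was still present at six months.

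The cost is one contrast per self-report outcome, or one reworded sentence, with no new data. The drawback is that durability may have to be described as not established for some outcomes.
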